Study Type	Project 4 Testing preliminary efficacy of a program to reduce barriers to community participation. Translational Trial Phase I Allocation: Randomized Intervention model: Parallel Assignment Primary purpose: Community reintegration
Date of First Enrollment	November 3, 2020
Target Sample Size	50
Recruitment Status	Project 4, closed to recruitment
Primary Outcome(s)	
Project 4 Testing Preliminary Efficacy of a Program to Reduce Barriers to Community Participation: We will test the working hypothesis that an adapted program, focused on resolving environmental barriers and building self-management skills in the home and community, will be feasible and superior to usual care for daily activity performance and participation outcomes. The hypothesis is based on our previous work,^{2,3} the work of others,⁴⁻⁶ and our unpublished preliminary data.
 
Aim 1. Determine the acceptability and feasibility of the adapted program. We will conduct a process evaluation⁷ of this intervention to evaluate the acceptability and feasibility and to aid in the interpretability of the trial. We will test the hypothesis that the adapted program will have high acceptability (80% retention), high fidelity by therapists (95% of elements and 90% of dose delivered), low safety risk (no increased rate of falls or health care use compared with control group), and high adherence (80% of modifications in use) at 6 months.
 
Aim 2. Estimate the magnitude of efficacy of the adapted program on the primary outcome of community participation (RNL) and on exploratory outcomes of daily activity performance and self-efficacy (I-HOPE) to select optimal end points for a large pragmatic trial. We will test the hypotheses that the adapted program is superior to usual care at 6 months on the primary and secondary end points.
 
Time Points of Interest: Baseline, 1 month

ORGANIZATIONAL STRUCTURE AND RESPONSIBILITIES

Principal Investigator:

[name], OTR/L

Responsibilities include: Managing the operations of the study, ensuring tasks are completed, ensuring compliance with quality-assurance requirements (e.g., human participant protection), preparing interim reports, and publication of study reports.

Study Coordinators:

[name], MSOT, OTR/L and [name], OTD, OTR/L

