The conceptual model of the intervention (Figure 3). The ICF describes the mechanism of the adapted program. PAwLTPD have a health condition that affects their body structure and function. The home and community environments of PAwLTPD pose barriers that prevent successful and safe performance of daily activities and participation. Intervening to remove barriers and enable PAwLTPD to use problem-solving strategies to overcome barriers will improve daily activity performance and participation outcomes. This conceptual model is empirically supported by our recent work exploring the role of environmental barriers in function.¹⁰¹

Baseline Home Visit (T1) for all Participants
Outcomes (primary endpoints described in Table 2) will be assessed by blinded evaluators at baseline and 6 months. Additional exploratory outcome measures are listed under the assessments section.

Baseline and 6-month follow-up assessments will be conducted in the home by a trained and certified rater blinded to group allocation. Follow-up assessments will be completed by a blinded rater who did not conduct the T1 evaluation, as new home modifications could reveal group assignment.

Intervention

The occupational therapists will deliver the final adapted program in each participant’s home and community. The essential elements include resolving barriers in the home and community and self-management skills to identify and resolve barriers. The intervention will target barriers in the home initially. Participants will identify target activities they want to address. Although problem areas addressed are participant-specific (tailored), the process to identify and address the problems is systematic and reproducible. All participants will receive identical intervention components (see Table 1).

Waitlist Attentional Control Treatment. The waitlist control group will receive the adapted program after the 6-month follow-up is completed. Participants in the waitlist control group will receive interview visits (equivalent in time by an occupational therapy graduate assistant). After the six-month follow-up has been completed, participants in this group will be contacted and asked to participate in a validity check. They will then be offered treatment at the end of the follow-up period.

Follow-Up Periods

[figure not shown]

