Figure 3. Adapted program conceptual model adapted from the ICF. Blue boxes represent intervention. Blue lines and green boxes represent the hypothesized mechanism of action. By reducing environmental barriers, activity and participation outcomes will improve.

Table 2. Measures: Primary End Points and Rationale for Inclusion

Reintegration to Normal Living Index (RNLI) ^{48,102-105}	The RNLI measures the extent to which a person is able to complete normal life activities. The 11-item measure quantifies participation. The administration of the RNLI is quick and simple. Individual item scores are converted to 100. The RNLI can be administered in person or by mail.
In-Home Occupational Performance Evaluation (I-HOPE) ¹⁰⁶	The I-HOPE is a performance-based assessment that can measure the performance of the environmental barriers that influence 42 activities performed in the home (person-environment fit). The tool also has a self-efficacy subscale that measures confidence performing activities. The instrument yields 4 subscales with high internal reliability ($\alpha = 0.77-0.78$) and interrater reliability (0.94 to 1.0). ¹⁰⁶ The I-HOPE will yield home assessment information and outcome activity performance assessment

6-month follow-up assessments will be conducted in the home by a trained and certified rater blinded to group allocation. Follow-up assessments will be completed by a blinded rater who did not conduct the T1 evaluation, as new home modifications could reveal group assignment.

Program Revisions

Based on data from our prior cohort study and focus groups, we will produce adapted program materials that maintain the “essential ingredients” of the program but are culturally tailored and deployable within the limits of current CILs and the Aging Services Network. We will develop a new set of materials including procedures and an interventionists’ manual.

To ensure fidelity to the original program, draft materials will be reviewed by [name] (developer of the original program) to ensure that the “essential elements” are maintained in the program. We will use the ecological validity and sensitivity framework⁶⁹ to document changes.

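### The documents name three different sets of primary outcomes, and the entry that makes RNL primary gives a time point and comparator that do not match the described trial

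*Combined protocol and SAP*

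**What the plan says.** **Outcome.** In the Primary Outcome(s) entry, Aim 2 is to estimate efficacy "on the primary outcome of community participation (RNL) and on exploratory outcomes of daily activity performance and self-efficacy (I-HOPE"). It then hypothesises that the program is "superior to usual care at 6 months on the primary and secondary end points". No outcome in the documents is labelled secondary.

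The section on the baseline home visit says "Outcomes (primary endpoints described in Table 2) will be assessed by blinded evaluators at baseline and 6 months". The table it points to is headed "Table 2. Measures: Primary End Points and Rationale for Inclusion" and has two rows, RNLI and I-HOPE. Under Assessments, the primary heading covers I-HOPE, RNLI and Westmead; the exploratory heading starts only after Westmead.

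**I-HOPE scores.** Table 2 says "The instrument yields 4 subscales with high internal reliability", while Assessments lists five. Table 2 refers to activity performance as the outcome use of the instrument, but no section formally designates a subscale.

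**Time.** The Primary Outcome(s) entry closes with "Time Points of Interest: Baseline, 1 month". Aim 2 in that entry, the baseline visit section and Assessments all place outcome measurement at 6 months. The Aim 2 analysis text refers to more than two time points for RNLI and I-HOPE and to 6 months after intervention. The Table 4 notes mention a 12-month follow-up.

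**Comparator.** The entry's hypotheses refer to usual care. The control section says "Participants in the waitlist control group will receive interview visits (equivalent in time by an occupational therapy graduate assistant"), with the program offered after the 6-month follow-up.

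**The concern.** The primary outcome determines which result the trial is read on. Here the same instrument is exploratory in one section and primary in two others, and Westmead is primary in only one. A reader following Aim 2 and a reader following Table 2 or Assessments would report different primary results from the same data, each with textual support. If RNLI were not positive and I-HOPE or Westmead were, the later sections would allow the favourable result to be presented as primary.

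This carries forward, because Aim 2 uses the results to select end points for a larger trial. The time point and comparator of the hypothesis are also unclear: a contrast with time-matched visits does not by itself demonstrate superiority to usual care.

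**Working it through.** **1. The plan's own figure.** Sample Size Calculations gives environmental barrier changes of 26.28 (SD 18.03) and 10.09 (SD 22.27), two-sided 5%, 80% power, and 25 per group.
- Difference: 26.28 − 10.09 = 16.19.
- SD: √((18.03² + 22.27²)/2) = 20.26. Standardised difference: 16.19/20.26 = 0.80.
- The normal approximation, n = 2(1.960 + 0.842)²/0.799² = 24.6, rounds up to 25 per group and matches the plan. An exact unequal-variance t calculation gives 79.0% power at 25 per group and needs 26 for 80%.

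The figure reproduces. It does not settle the hierarchy, because the variable is environmental barriers and not RNLI, and the section names no instrument for it.

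**2. The sections side by side.**

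| Place | RNL/RNLI | I-HOPE | Westmead |
|---|---|---|---|
| Aim 2, Primary Outcome(s) entry | primary | exploratory | not named |
| Baseline visit section and Table 2 | primary | primary | not listed |
| Assessments | primary | primary | primary |

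No reading of the three rows makes them agree.

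**3. Time and comparator.** Scheduled rater assessments are at baseline and 6 months, which is two time points. Monthly contacts exist, but they collect falls and health care use. After the 6-month follow-up, "participants in this group will be contacted and asked to participate in a validity check", but that contact is not said to collect RNLI or I-HOPE; nor is the 12-month follow-up in the Table 4 notes. So neither 1 month nor more than two time points matches the described schedule. Treatment visits run over 8 weeks (Table 1), so 6 months after intervention is not clearly the same as the 6-month assessment. The described control arm is a waitlist with attention visits, not usual care alone.

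**4. Size of the error opportunity.** Take the three scores Aim 2 names: RNLI, I-HOPE performance and I-HOPE self-efficacy. Assume no true effect, unadjusted two-sided 5% tests and equal pairwise correlation r. The documents give no correlation, so r runs from 0 to 0.7.

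At r = 0:
- At least one p<0.05: 1 − 0.95³ = 14.3%.
- At least one p<0.05 favouring the program: 1 − 0.975³ = 7.3%.
- RNLI p≥0.05 with at least one of the two I-HOPE scores favouring the program: 0.95 × (1 − 0.975²) = 4.7%.

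For correlated scores, using the equicorrelated normal distribution:

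| r | Any p<0.05 | Any favouring program | RNLI not significant, I-HOPE favouring |
|---|---|---|---|
| 0 | 14.3% | 7.3% | 4.7% |
| 0.3 | 13.6% | 6.8% | 4.3% |
| 0.5 | 12.5% | 6.3% | 3.8% |
| 0.7 | 10.9% | 5.5% | 3.0% |

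The one-score benchmarks are 5% for the first column and 2.5% for the second. Westmead is not included.

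**The case against.** The strongest reply is that this is a 50-person pilot. It sets out to estimate magnitude and examine a series of measures, and it says that statistical significance is not its goal. That stands as a reason to temper the severity. It does not remove the problem: the Primary Outcome(s) entry and the Aim 2 analysis text both state superiority hypotheses, the analysis focuses on the significance of the group-by-time interaction, and an estimation study also needs one identified primary outcome.

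A second reply is that Table 2, the working hypothesis and the Aim 2 analysis all point to daily activity performance, so I-HOPE is less open-ended than its subscale count suggests. This is fair, and it is why the calculation uses only the two I-HOPE scores Aim 2 names. A two-primary reading also has some textual support, since the working hypothesis covers both activity performance and participation. The sponsor should therefore be free to document a different prespecified hierarchy.

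On the comparator, the control arm is named and described, so a correction of the label is enough. On timing, 6 months appears repeatedly and 1 month once. A reader might suppose that 1 month refers to a mailed RNLI, because participants return that form by post. The documents give the mode of return but no such time point, so this is speculation.

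**Conclusion.** The contradiction is confirmed in the current text: three primary sets, a secondary tier with no members, and a time point and comparator that conflict with the described assessments and control arm. The plan is wrong as written on its primary outcome. The statistical size is moderate: an 11–14% chance of at least one nominally significant score among three under no effect, and 3.0–4.7% for the specific case of a non-significant RNLI with a favourable I-HOPE score. Both ranges rest on assumed correlations of 0 to 0.7 and unadjusted tests; the textual conflict depends on neither.

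A reader might infer that, because the trial is sized on environmental barriers, a positive I-HOPE result with a non-significant RNLI is likely if the program works as planned. The documents do not support this. They give no RNLI effect and do not say that the sample-size variable is an I-HOPE score. The plan's own conceptual model also expects barrier removal to improve participation. Any such probability would be driven by the RNLI effect one chose to assume.

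**What to change.** Issue a dated amendment before outcomes are analysed by arm, or disclose in it that by-arm results had already been seen. This matters because recruitment is closed and semi-annual efficacy review with interim analyses is planned. In it:

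- Apply Aim 2's hierarchy in every section, with RNLI at the 6-month assessment as the single primary outcome. If the sponsor can document that a different hierarchy was prespecified, state that one instead.
- Relabel I-HOPE and Westmead as exploratory in Table 2 and Assessments, reported with 95% confidence intervals and not as primary evidence of efficacy.
- Name the I-HOPE subscales to be analysed, correct their number, and state the role of the environmental barrier score if it is the sample-size variable.
- Delete the reference to secondary end points, or define them.
- Reconcile the 1-month entry, the reference to more than two time points, the phrase about 6 months after intervention and the 12-month note in Table 4 with the schedule actually used.
- In the Primary Outcome(s) hypotheses, replace usual care with waitlist attention control.

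The cost is wording and an amendment record; no new data or participants are needed. Fewer outcomes can then be called primary.

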Participants will be allocated using a 1:1 ratio by block randomization sequences generated a priori using a computerized probability model. The allocation ratio will be maintained at periodic intervals. Groups will be balanced for race and sex. Randomization sequence concealment will be achieved by research electronic data capture (REDCap)⁸³ after baseline assessment.

Consent

CONFIDENTIAL: This document is the intellectual property of the CEDAR Midwest research group. Acceptance of this document constitutes the agreement by the recipient that no unpublished information contained herein will be published or disclosed without prior written approval. 11

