First, we will examine the distributional characteristics of study variables (outcomes, covariates). Basic descriptive statistics for each measure and the intercorrelations among study variables will provide a simple initial view of the sample characteristics (demographic and health-related variables). Second, we will determine whether participants are representative of the eligible population by comparing baseline sociodemographic characteristics (eg, age, gender, education) of the study population with those eligible to participate in the study but who declined to participate. Continuous variables will be analyzed with the appropriate parametric methods (eg, *t* test) to test for differences between the participants in the study and those who refused. Discrete variables will be analyzed with the appropriate nonparametric test (eg, chi-square test of association) to test for differences between the participants in the study and those who refused.

Next, we will use unpaired *t* tests and chi-square tests to compare baseline characteristics in the 2 groups for descriptive information (except when statistical assumptions are not met, in which case we may use Wilcoxon or Fisher exact tests). We will examine the process data before the efficacy analyses.¹⁷⁰ The goal of Aim 1 is to examine the feasibility of conducting a larger trial by conducting a process evaluation. We will conduct between-group comparisons of process end points collected at 6 months (eg, health care utilization rate, safety, dosage delivered, and adherence rate) using unpaired *t* tests or chi-square tests. We will compare the characteristics of patients that complete the assigned intervention to those who do not for differences in disability severity and comorbidities. Descriptive statistics will be used for costs per participant and adherence.

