The goal of Aim 2 is to test the hypothesis that the adapted program will result in greater improvements in participation and daily activity performance than control at 6 months after intervention. Mixed-model repeated-measures analysis of variance will be used for longitudinal analyses of variables measured at >2 time points (ie, Reintegration to Normal Living Index, I-HOPE). The focus of this analysis will be the significance of the interaction between group and time. Hypotheses will test for interactions in terms of the equality of changes over time in the 2 groups. Contrasts will be used in testing the null hypothesis that changes between 2 specific time points in one group are equal to corresponding changes in the group. I-HOPE scores will be analyzed with analysis of covariance with the 6-month value as the dependent variable and the baseline value as the covariate. For all analyses, we will determine whether required distributional and model-specific assumptions are satisfied. To explore the potential trial end points, we will select the best independent indicator of participation and compare the measures for sensitivity and statistical efficiency with data collected at 6 months after intervention.

Sample Size Calculations

Although statistical significance is not the goal of this study, we estimated a sample size using a power analysis for a 2-sided, 2-sample, unequal-variance *t* test using G*Power with a significance level of 5% and power of 80%.¹⁷³ The sample size calculation includes a correlation between baseline and follow-up measures and is based on analysis of change scores, which is equivalent in efficiency to the proposed analytic model. Data were used from a pilot study with a total of 113 community-dwelling older adults.¹⁰⁰ We estimated the sample size for the mechanism of action (reducing environmental barriers). Environmental barrier mean changes in intervention and control groups were 26.28 (SD 18.03) and 10.09 (SD 22.27), respectively. A sample size of 50 (25 in each group) is needed to provide 80% power.

Potential Benefits, Risks and Alternatives

Benefits

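### Race and sex are balanced at randomization but left out of the Aim 2 models; adding them is a nearly free change with a modest expected gain in precision

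*Combined protocol and SAP*

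**What the plan says.** Under Randomization and Blinding: "Participants will be allocated using a 1:1 ratio by block randomization sequences generated a priori", and "Groups will be balanced for race and sex". The section does not say how the balance is achieved (strata or minimization), what the block size is, or how race is coded.

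Under Covariates, race/ethnicity and sex appear among the demographics to be collected. No model in the plan draws on that list.

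Under Statistical Analyses, the Aim 2 outcomes are handled in two ways. A repeated-measures mixed model for the RNLI and I-HOPE tests the group-by-time interaction. I-HOPE is also analysed by "analysis of covariance with the 6-month value as the dependent variable and the baseline value as the covariate". Neither names race or sex. The Aim 1 process measures get simple two-group tests: "We will conduct between-group comparisons of process end points collected at 6 months".

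Sample Size Calculations describes a "power analysis for a 2-sided, 2-sample, unequal-variance" t test on change in environmental barriers, and concludes: "A sample size of 50 (25 in each group) is needed to provide 80% power".

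**The concern.** Restricting the randomization on race and sex removes most of the chance imbalance in those factors from the treatment contrast, so the estimated difference varies less from trial to trial. A model that omits the factors cannot see this. Their variance stays in the residual, and the reported standard error describes a less precise trial than the one that was run.

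At stake is the width of the Aim 2 intervals in a 50-person study. Aim 2 is meant to estimate the size of the effect and to choose end points for a larger trial, partly by comparing the measures on statistical efficiency. If race and sex relate more strongly to one measure than to another, leaving them out overstates the error by different amounts and could blur that comparison. The residual SDs passed to the next sample size calculation would also be somewhat too large.

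**Working it through.** **1. The plan's own figure.** Input: "Environmental barrier mean changes in intervention and control groups were 26.28 (SD 18.03) and 10.09 (SD 22.27), respectively".

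- Difference: 26.28 − 10.09 = 16.19.
- Root-mean-square SD: √[(18.03² + 22.27²)/2] = 20.26. Standardized difference: 16.19/20.26 = 0.80.
- Normal approximation, two-sided 5%, 80% power: n per arm = 2(1.96 + 0.84)²/0.80² = 24.5, so 25 per arm and 50 in total. The stated size reproduces. Power at 25 per arm is 0.807 by this formula and 0.790 by the exact Welch t calculation.

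**2. Why the standard error is too wide.** Let σ be the SD of the analysed quantity and R² the share of its variance explained by race and sex. With full balance and n per arm, the difference in means has true variance (1 − R²)σ²·2/n, whereas the unadjusted analysis estimates σ²·2/n. The reported standard error is therefore too large by a factor of 1/√(1 − R²).

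- Unadjusted: 20.26 × √(2/25) = 5.73.
- R² = 0.10: factor 1.054. R² = 0.20: factor 1.118. R² = 0.30: factor 1.195.

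Real blocks leave some strata incomplete, so the actual excess is slightly smaller.

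**3. Simulation.** Assumed: 50 participants, two race levels by two sexes, permuted blocks of 4 in each stratum, 6,000 trials per setting, difference 16.19, SD 20.26. Monte Carlo error is about √(0.05 × 0.95/6000) = 0.3 points for type I error and √(0.8 × 0.2/6000) = 0.5 points for power. The SE columns are from the runs under no treatment effect.

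| R² of analysed quantity | Reported SE, unadjusted | True SD of estimate | Type I error, unadjusted / adjusted | Power, unadjusted / adjusted |
|---|---|---|---|---|
| 0 | 5.70 | 5.75 | 5.5% / 5.5% | 79% / 79% |
| 0.05 | 5.70 | 5.65 | 5.0% / 5.2% | 79% / 81% |
| 0.10 | 5.70 | 5.49 | 4.2% / 5.2% | 80% / 83% |
| 0.20 | 5.72 | 5.16 | 2.8% / 5.0% | 82% / 88% |
| 0.30 | 5.71 | 4.90 | 2.2% / 5.2% | 83% / 91% |

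Repeat runs under the same assumptions put the excess in the standard error at about 4 to 6% for R² = 0.10 and 10 to 11% for R² = 0.20. Power at R² = 0.20 was 81–82% without the factors and 86–88% with them.

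**4. Which R² applies.** The R² above is for the quantity analysed, not for the raw score. Suppose race and sex shift the score by the same amount c at both visits.

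- *Group-by-time test.* With baseline and 6-month visits this is a comparison of change scores, and c − c = 0. R² for change is zero however strongly the factors relate to the score. Simulated with R² of 0.10 or 0.20 in the raw score, power is 79% with and without the factors.
- *Analysis of covariance.* With equal variances at the two visits and correlation ρ, the share left after baseline is [R²/(1 − R²)] × [(1 − ρ)/(1 + ρ)]. The sample size section mentions a baseline-to-follow-up correlation but gives no value; 0.5 and 0.7 are assumed here. For raw R² = 0.10: 0.111 × 0.333 = 0.037 and 0.111 × 0.176 = 0.020. For raw R² = 0.20: 0.25 × 0.333 = 0.083 and 0.25 × 0.176 = 0.044.
- *Simulated covariance analysis* (effect 0.8 SD of the analysed quantity), unadjusted against adjusted power. Raw R² = 0.10: 77.8% against 78.5% (ρ = 0.5) and 78.4% against 78.8% (ρ = 0.7). Raw R² = 0.20: 79.6% against 81.2% and 79.0% against 79.8%. Unadjusted type I error was 4.3 to 4.8%.

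**The case against.** The case against giving this much weight has four parts.

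- **The larger losses need a strong assumption.** They arise only if race and sex explain 10 to 20% of change, or of the 6-month value given baseline. That means they predict how people respond over time, and nothing in the documents suggests it. This stands. A reader might infer that precision is lost as soon as race or sex is related to the outcome. Step 4 shows that this is false for the group-by-time test when the relation is stable, and nearly so for the covariance analysis.
- **The error is in the safe direction.** This stands. A reader might infer that the analysis is biased, that its type I error is inflated, or that the omission pulls power below plan. None of these follows. Unadjusted power in the table is never below the 79% seen when race and sex explain nothing. The loss is relative to the adjusted analysis only.
- **This is a pilot whose authors say significance is not its goal.** That lowers the weight of a conservative test. It does not remove the point, because interval width and the comparison of end points depend on the same standard errors, and the plan still tests the interaction.
- **The balancing mechanism is not described.** True: stratified blocks of 4 and two race levels are assumptions. With more race levels, adjustment costs more degrees of freedom and some cells become sparse at N = 50.

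The Aim 1 and baseline comparisons are also unadjusted, but they are descriptive or concern process measures. They give no good reason to extend the point to them.

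**Conclusion.** The point holds as a modest one. Allocation is balanced on race and sex, both are already collected, and the Aim 2 models use neither. The consequence is standard errors that are somewhat too wide and conservative tests, in proportion to how well the two factors predict the analysed quantity.

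The documents do not give that share. Over an assumed range it runs from no loss (effects constant over time, group-by-time test), through about 0 to 2 power points (constant effects, analysis of covariance), to about 3 points at R² = 0.10 and about 5 to 6 points at R² = 0.20 of the analysed quantity. When the factors explain nothing, adjusting has no visible cost at N = 50. This is a free improvement with a modest expected gain, not a flaw that threatens the validity of the trial.

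**What to change.** In the Aim 2 paragraph of Statistical Analyses:

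- Add race and sex, coded as used in the randomization, as fixed covariates beside baseline in the I-HOPE analysis of covariance.
- In the mixed model for the RNLI and I-HOPE, add race and sex with their time interactions. With complete data, main effects alone leave the group-by-time contrast unchanged.
- Report the adjusted difference with its 95% confidence interval as the main result, and the unadjusted result as a sensitivity analysis.
- State under Randomization and Blinding how the balance is produced and how race is coded, so that the model can match it. Pool sparse race levels by a rule set before analysis.

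Leave the descriptive and Aim 1 process comparisons as they are.

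The cost is a few sentences of wording and about two degrees of freedom, more if race has more than two levels. No extra data, visits or participants are needed. Fixing the covariates before analysis also closes off choosing them afterwards.

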We will conduct a trial to reduce the “science to service” gap using the CBRN.^{70,71} Hybrid designs examine efficacy while conducting a process evaluation of an intervention.⁷² We anticipate that a hybrid approach will lead to more rapid translational gains in intervention uptake, more effective implementation strategies, and more useful information for decision makers. We will facilitate translation by “designing for implementation and dissemination”⁷³ to ensure that findings are useful, relevant, and ready for widespread dissemination.⁷⁴ We will use the RE-AIM framework⁶⁷ (Figure 2) to adapt the intervention, to design the trial, and to plan for potential future dissemination through the CBRN.⁷⁵ Cost is an important factor that influences decisions and uptake of interventions.⁷⁶ To evaluate potential for implementation, we will examine costs to deliver the intervention, with engagement of CBRN members. This approach will provide CBOs with a better understanding of the impact of an intervention and incorporate RE-AIM metrics to aid in understanding the translation and sustainability of the program.

[figure not shown]

Figure 2. RE-AIM framework used to adapt the program

Study Participants

Recruitment

The eligibility criteria include (1) age 45-65 years; (2) self-report of difficulty with ≥ 2 daily activities using the OARS ADL scale⁸¹; and (3) onset of a physical disability 5 years prior to participation (eg, SCI, cerebral palsy, post-polio syndrome, stroke, amputation). We will exclude those currently institutionalized.

To ensure that the sample represents people that this program will target in the future (reach),⁸² we will select a sample of 50 adults aging with a long-term disability from the St. Louis members of the CBRN or who have participated in our previous cohort study of PAwLTPD. The CBRN offers access to PAwLTPD who are hard to reach in the traditional health care system and who could benefit from the intervention. In the current cohort of SLAAA participants, 2526 are aged 45-65 years (people with disabilities). Paraquad serves 420 people with physical disabilities aged 45-65 years who meet the eligibility criteria. We will invite eligible participants to participate by telephone. All recruitment and study materials will be IRB approved.

Randomization and Blinding

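### The plan sets out to determine whether the sample is representative using only tests of difference from decliners, which cannot establish similarity

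*Combined protocol and SAP*

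**What the plan says.** The first paragraph of Statistical Analyses states the purpose: "we will determine whether participants are representative of the eligible population by comparing baseline sociodemographic characteristics". The comparison group is "those eligible to participate in the study but who declined to participate". Continuous characteristics go to a parametric test such as the t test, and discrete ones to a test such as chi-square, in each case "to test for differences between the participants in the study and those who refused". For this comparison the plan gives no measure of the size of a difference, no confidence interval, no significance level and no rule for reading a null result.

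The Recruitment section explains why the answer matters. The participants are drawn from the community network or an earlier cohort for this purpose: "To ensure that the sample represents people that this program will target in the future (reach". It fixes the number: "we will select a sample of 50 adults aging with a long-term disability". The Process Evaluation section and Table 4 add recruitment and retention rates, demographics of eligible people and reasons for declining, but no other criterion for calling the sample representative.

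**The concern.** The question asked and the tool supplied do not match. To say that participants represent the eligible population is to say that any differences are small. A test of difference can find evidence that groups differ. When it does not, the cause may be similarity or may be too few people, and the p-value does not separate the two. With one group fixed at 50, too few people is a serious possibility.

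The next paragraph of the plan labels the comparison of baseline characteristics between the two arms as descriptive. The decliner comparison carries no such label and is there to settle a question. At stake is the pilot's statement about whom it reached, which would inform recruitment for the definitive trial that the process evaluation is meant to prepare.

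**Working it through.** **Is there a figure in the plan to reproduce?** Not for this comparison. The only power calculation concerns change in environmental barriers between arms. It reproduces: difference 26.28 − 10.09 = 16.19; SD = √[(18.03² + 22.27²)/2] = 20.26; standardised difference 0.799. The normal approximation gives 25 per arm, 50 in all. So 50 was chosen for a large between-arm effect, not for detecting small differences from decliners.

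**Inputs.** Participants n₁ = 50 (Recruitment). Two-sided 5% is an assumption here, borrowed from Sample Size Calculations. The number of decliners, m, is not given, so it is varied. For scale, the Recruitment section names pools of 2,526 and 420 people; 2,526 + 420 − 50 = 2,896, if the pools do not overlap. The larger pool is described only by age and disability, so the number eligible and approached would be far smaller.

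**Continuous characteristics.** Power comes from the noncentral t distribution with λ = d·√[50m/(50 + m)] and 48 + m degrees of freedom. A difference is missed with probability 1 − power.

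| Decliners m | λ, d = 0.3 | Power | Missed | λ, d = 0.5 | Power | Missed |
|---|---|---|---|---|---|---|
| 25 | 1.225 | 0.227 | 77% | 2.041 | 0.522 | 48% |
| 50 | 1.500 | 0.318 | 68% | 2.500 | 0.697 | 30% |
| 100 | 1.732 | 0.406 | 59% | 2.887 | 0.818 | 18% |
| 2,896 | 2.103 | 0.557 | 44% | 3.505 | 0.939 | 6% |

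The 0.3-SD miss rate hardly falls further however many decline, because the 50 participants limit the precision.

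**Binary characteristics.** These use exact binomial enumeration of the pooled two-proportion test, with 50% of participants against 70% of decliners:

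| Decliners m | Power | Missed |
|---|---|---|
| 25 | 0.404 | 60% |
| 50 | 0.546 | 45% |
| 100 | 0.668 | 33% |

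These figures are for prevalence near 50%, where variance is greatest. Away from 50% the test does better. For a 15-point difference with 100 decliners, power is 0.43 for 65% against 50%, but 0.81 for 80% against 95%. The documents give no expected split by race or gender, so neither case can be called typical.

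**What an interval would show.** The approximate 95% half-width is 1.96·√(1/50 + 1/m) in SD units, and 1.96·√(0.25/50 + 0.25/m) for a proportion near 50%.

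| Decliners m | SD units | Points |
|---|---|---|
| 50 | 0.39 | 20 |
| 100 | 0.34 | 17 |
| 2,896 | 0.28 | 14 |

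**The case against.** The strongest reply is that the plan never says a non-significant result proves representativeness. That is correct. A reader might infer such a rule from the pairing of purpose and method, but the text states no threshold and no reading of a null result. What stands is narrower: the plan promises a determination and supplies no means of reaching a positive one.

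Second, reach does not rest on these tests. Table 4 defines it by recruitment rate, retention rate and reasons for not enrolling, and demographics of eligible people are monitored, so a sizeable gap could be seen descriptively. This lowers the stakes. It does not supply a criterion for the word representative.

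Third, the tests are not weak for everything. A 0.5-SD difference is detected 82% of the time with 100 decliners. It is also tempting to say that a 15-point difference in a binary characteristic is usually missed whatever the number of decliners; the 80% against 95% case shows that this fails away from 50% prevalence.

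A reader might also extend the point to the comparison of those who complete the intervention with those who do not. The plan attaches no similarity claim and no named test to that comparison, so the criticism does not carry over.

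**Conclusion.** The point holds in a limited form. The stated method cannot support the stated conclusion, and nothing elsewhere in the document fills the gap. The risk of overlooking a real difference is substantial for differences of about 0.3 SD at any number of decliners, for 0.5 SD when there are about 50 decliners or fewer, and for 20 points near 50% prevalence across the 25 to 100 decliners examined. These figures assume a two-sided 5% level and a number of decliners that the plan does not give.

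The consequence is confined to what the pilot may say about reach and generalisability. Randomisation, the outcome analyses, the numerical feasibility targets and the sample size are untouched. It is a minor improvement, worth making because it is easy.

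**What to change.** In the first paragraph of Statistical Analyses:

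- Replace the participant-versus-decliner tests with the standardised difference (continuous) or difference in proportions (discrete) and its 95% confidence interval for each characteristic.
- Replace the undertaking to determine representativeness with one to describe how participants differ from eligible decliners.
- Add that a non-significant difference will not be read as representativeness, and report the number of decliners with data on each characteristic.

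A formal similarity margin is not recommended. With 50 decliners the interval for a proportion near 50% is already about ±20 points, so a margin of that size could be met only if the observed difference were almost nil. Any margin would also be arbitrary, since the documents give no basis for one.

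The cost is two or three sentences. No new visits are needed, and closed recruitment is no obstacle. Gender, birthdate and race are listed for recruitment tracking; education, which the plan names as an example for this comparison, is not, so its availability for decliners should be checked. The downside is wide intervals, so the report will often have to say that similarity was not shown.
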